### 5 Study Design

### 5.1 Overall Study Design and Plan

Phase I study for IA injection, double-blind, placebo-controlled, randomized, multicenter, single ascending dose is designed to assess the safety, tolerability and pharmacokinetic of 4P004 in participants with target knee OA KL 2-4.

Participants were enrolled in 4 cohorts; in each cohort participants receive either 4P004 or placebo (6:2).

For the highest dose cohort, a sentinel dosing was planned and implemented.

Recruitment of participants

Participants are recruited via investigators' patient registry or via advertising.

- A Screening visit at D-7 (D-14 to D-4) is performed at study site and if the participant still agrees to participate in the study after the investigator has answered all his/her questions, the participant will sign the informed consent form.
   This visit should take place 4 to 14 days before the randomization day. During this visit, the eligibility of the participant will be evaluated.
- The Randomization visit (Day 1 to Day 2) is performed at study site and the participant is randomized in the study after review of inclusion & exclusion criteria. The participant will be hospitalized for 24 hours. The IMP IA injection will be performed by the investigator after a venous infusion line has been set up. Participant will be monitored during the 24-hour hospitalization and will be discharge on D2.
- The Follow-up visit at D4 (±1 day) is a virtual visit by phone call unless abnormal, clinically significant findings are observed upon discharge or at the investigator's discretion (participants should then be brought back to the clinic for re-evaluation).
- The Follow-up visit at D8 (±2 days) is a face-to-face visit. Participant will be asked to fill in a diary and a NRS questionnaire up to Day 29 to record any AE (in particular pain in the target knee) and analgesic medication taken.
- The End of Study (EoS) visit at D29 (±2 days) is a virtual visit by phone call unless abnormal, clinically significant findings are observed upon discharge or at the investigator's discretion (participants should then be brought back to the clinic for re-evaluation). Participant will be asked to send back to the Investigator the diary and the NRS questionnaire.

An independent Data and Safety Monitoring Board (DSMB) has been set up for this study and review safety data during the study. The DSMB is composed of 2 physicians specialized, one in rheumatology and one in diabetology. Members review the safety data in sessions on a regular basis during the study, and at any time if any SAE at least possibly related to liraglutide or safety issue occurs.

### 5.2 Method of Treatment Assignment and Randomization

Participants are enrolled in 4 cohorts; in each cohort participants receive either 4P004 or placebo (6:2).

Randomization has been performed using a pre-established randomization list. This list has been generated by a statistician for the IMPs (4P004 or placebo) based on study design (sequential randomization according to the dose escalation and sentinel patients).

The randomization is requested by the site at visit 2 (on D1) after eligibility confirmation. Participants are assigned their treatment according to the randomization schedule in the order in which they are randomized into the study.

### 6 Sequence of Planned Analyses

#### 6.1 Interim Analyses

No interim analysis is planned.

#### 6.2 Final Analyses and Reporting

All final, planned, analyses identified in the protocol and in this SAP will be performed only after the last patient has completed the study. A data review meeting will be held prior to database lock and completion of the final analyses.

In addition, no database may be locked, or analyses completed until this SAP has been approved.

Key statistics and study results will be made available following database lock and prior to completion of the final clinical study report (CSR).

Any, post-hoc, exploratory analyses completed to support planned study analyses, which are not identified in this SAP, will be documented and reported in appendices to the CSR. Any results from these unplanned analyses will also be clearly identified in the text of the CSR.

### 7 Sample Size Estimation

The sample size was not based on statistical power considerations. The sample size for this study of 8 participants in each cohort (6 active : 2 placebo) is considered to be sufficient for evaluation of safety, tolerability, and PK of each cohort.

### 8 Analysis Populations

The following analysis populations are defined for the study:

- Safety population: The safety analysis set will consist of all participants who are enrolled and received 1 dose of study drug.
- PK population: The Pharmacokinetics (PK) analysis set will consist of all participants who receive study drug and have at least 1 measurable plasma concentration. Placebo subjects will not be part of the PK population.

Unless otherwise stated, all analyses will be done on the Safety population.

### 9 General Principles for Statistical Analysis

Data will be summarized using classical descriptive statistics for the following groups:

- pooled placebo (i.e. participants receiving placebo in any cohort),
- each 4P004 dose level,
- unplanned doses if any (see below),
- 4P004 overall

A group "All" (Placebo + 4P004 overall) will be added if explicitly mentioned.

Categorical data will be presented using counts and percentages of subjects, while continuous variables will be presented using the mean, standard deviation, median, minimum, maximum, and number of observations with non-missing values. The coefficient of variation [%CV] will be provided for PK parameters.

The safety evaluation will be based upon the review of the individual values and descriptive statistics. No statistical significance tests will be performed on safety data.

### 9.1 Analysis Software

Statistical analysis will be performed using SAS version 9.4 for Windows or later.

### 9.2 Methods for Withdrawals, Missing Data, and Outliers

Missing data will not be replaced. Analyses will be done on the maximum available observed data. If a PK point is missing at time t, an interpolation may be done, depending on data review.

#### 9.3 Planned and Actual Treatment

In cohort 3 one participant was underdosed; the Sponsor decided (blinded review) to include one more participant to ensure 6 participants with the right active dose; consequently a ninth participant has been included to receive the same treatment as the underdosed participant. Therefore, at least one subject may have an actual treatment different from the planned one (if the underdosed subject did not receive placebo).

Participants who did not receive the planned treatment will be assigned, upon review of their actual treatment, to either of the following actual arm:

if the received treatment is one of the planned ones, or close enough, to the corresponding arm

otherwise, to an arm "4P004 unplanned"

Unless stated otherwise, analyses will be presented by actual arm.

### 9.4 Derived and Computed Variables

For any variable, the baseline value is defined as the last observation before IMP injection.

The time will be split into 3 periods (epochs):

- before treatment (screening)
- during treatment (from IMP injection to 7 days after IMP injection date)

after treatment

The following PK parameters will be calculated from measured plasma concentrations for each participant:

- Maximum observed concentration (Cmax)
- Time of maximum observed concentration (Tmax)
- Area under the curve (AUC0-t)
- Terminal Half-life (T1/2)

### 10 Study Subjects

### 10.1 Disposition of Participants and Withdrawals

**Table TTT. Participant disposition** 

	Placebo	4P004	4P004	4P004	4P004	4P004	All
	(pooled)					(pooled)	
Screened Participants							XX
Randomized Subjects 	XX	XX	XX	XX	XX	XX	XX
Treated Subjects 	XX	XX	XX	XX	XX	XX	XX
Completed Subjects 	XX	XX	XX	XX	XX	XX	XX
Withdrawn Subjects 	XX	XX	XX	XX	XX	XX	XX
Reason 1	XX	XX	XX	XX	XX	XX	XX
•••	XX	XX	XX	XX	XX	XX	XX

<sup>1 by planned treatment

#### 10.2 Protocol Violations and Deviations

Protocol violations and deviations are not described in the protocol, and will be established by blind review.

Major deviations are defined as follows:

- non respect of inclusion criteria
- underdose
- overdose

All others will be considered as minor deviations.

### **Table TTT. Deviations by Category**

Major, Minor

Major deviations will be listed:

#### **Listing LLL. Major Deviations**

Subject Id, Treatment Group, Deviation Text

### 11 Demographics and Other Baseline Characteristics

All TFL in this section will include the column "All".

#### 11.1 Demographics

#### **Table TTT. Demographics and Baseline Characteristics**

Sex, Age, Weight, BMI, KL Grade, Pain at Visit 2 (mean of the previous 48h)

#### **Table TTT. Other Baseline Characteristics**

Height, Race

#### 11.2 Prior Medications

Medication will be coded using the WHO-ATC/DDD Index 2023.

All tables in this section will be sorted by descending percentages in the column "4P004 (pooled)".

Medications will be flagged with 3 flags:

pre-treatment: treatment taken during screening

<sup>2 by actual treatment

- on-treatment: treatment taken during the treatment period
- post-treatment: treatment taken after the treatment period

In case of uncertainty, a medication will be assigned to all periods during which it might have been taken.

Medications not classified as pain killer vs. other medications will be assigned to one of the two categories for analyses, based on medical review by the Sponsor

Table TTT. Pain killers started and ended before treatment

ATC Level 2	Placebo	4P004	4P004	4P004	4P004	4P004	All
	(pooled)					(pooled)	
	(N=XX)						
Any pain killer	XX (XX.X%)						
ATC 2 term	XX (XX.X%)						
ATC 2 term	XX (XX.X%)						

Table TTT. Other medications started and ended before treatment

ATC Level 2	Placebo	4P004	4P004	4P004	4P004	4P004	All
	(pooled)					(pooled)	
	(N=XX)						
Any medication	XX (XX.X%)						
ATC 2 term	XX (XX.X%)						
ATC 2 term	XX (XX.X%)						

### 11.3 Medical History

All tables in this section will be sorted by descending percentages in the column "4P004 (pooled)".

**Table TTT. Medical History by SOC** 

SOC	Placebo	4P004	4P004	4P004	4P004	4P004	All
	(pooled)					(pooled)	
	(N=XX)						
Any Medical History	XX (XX.X%)						
SOC term	XX (XX.X%)						
SOC term	XX (XX.X%)						

## 12 Safety and Tolerability Analyses

#### 12.1 Concomitant Medications

All tables in this section will be sorted by descending percentages in the column "4P004 (pooled)".

Table TTT. Pain killers started before treatment and continuing at IMP injection

ATC Level 2	Placebo	4P004	4P004	4P004	4P004	4P004	All
	(pooled)					(pooled)	
	(N=XX)						
Any pain killer	XX (XX.X%)						
ATC 2 term	XX (XX.X%)						
ATC 2 term	XX (XX.X%)						
ATC 4 term	XX (XX.X%)						
()	XX (XX.X%)						

Table TTT. Other medications started before treatment and continuing at IMP injection

ATC Level 2	Placebo	4P004	4P004	4P004	4P004	4P004	All
ATC Level 4	(pooled)					(pooled)	
	(N=XX)						
Any medication	XX (XX.X%)						
ATC 2 term	XX (XX.X%)						
ATC 4 term	XX (XX.X%)						
()	XX (XX.X%)						
ATC 2 term	XX (XX.X%)						
ATC 4 term	XX (XX.X%)						
()	XX (XX.X%)						

Table TTT. Pain killers started during treatment

ATC Level 2	Placebo	4P004	4P004	4P004	4P004	4P004
ATC Level 4	(pooled)					(pooled)
	(N=XX)	(N=XX)	(N=XX)	(N=XX)	(N=XX)	(N=XX)
Any pain killer	XX (XX.X%)					

| ATC 2 term | XX (XX.X%) |
|------------|------------|------------|------------|------------|------------|------------|
| ATC 4 term | XX (XX.X%) |
| ()         | XX (XX.X%) |
| ATC 2 term | XX (XX.X%) |
| ATC 4 term | XX (XX.X%) |
| ()         | XX (XX.X%) |

Table TTT. Other medications started during treatment

ATC Level 2	Placebo	4P004	4P004	4P004	4P004	4P004
ATC Level 4	(pooled)					(pooled)
	(N=XX)	(N=XX)	(N=XX)	(N=XX)	(N=XX)	(N=XX)
Any medication	XX (XX.X%)					
ATC 2 term	XX (XX.X%)					
ATC 4 term	XX (XX.X%)					
()	XX (XX.X%)					
ATC 2 term	XX (XX.X%)					
ATC 4 term	XX (XX.X%)					
()	XX (XX.X%)					

### 12.2 Adverse Events

All tables in this section will be sorted by descending percentages in the column "4P004 (pooled)".

#### 12.2.1 Definitions

Adverse events will be classified in one of three categories:

- pre-treament: events that certainly started during screening
- post-treatment: events that certainly started after the treatment period
- treatment-emergent (TEAE): all other events

#### 12.2.2 Overview of TEAEs

This table will also show the number of AEs, as depicted below.

**Table TTT. Overview of TEAEs** 

	Placebo		4P004									
	(pooled)										(pooled)	
	(N=XX)		(N=XX)		(N=XX)		(N=XX)		(N=XX)		(N=XX)	
	Subjects	# 	Subjects	#1								
Any TEAE	XX (X.X%)	XX	XX (X.X%)	XX								
AESI	XX (X.X%)	XX	XX (X.X%)	XX								
SAEs	XX (X.X%)	XX	XX (X.X%)	XX								
by Toxicity Grade												
1 Mild	XX (X.X%)	XX	XX (X.X%)	XX								
2 Moderate	XX (X.X%)	XX	XX (X.X%)	XX								
by Relationship to Study Drug												
Not Related	XX (X.X%)	XX	XX (X.X%)	XX								
Unlikely	XX (X.X%)	XX	XX (X.X%)	XX								
()	XX (X.X%)	XX	XX (X.X%)	XX								
by Outcome												
Recovered	XX (X.X%)	XX	XX (X.X%)	XX								
Recovering	XX (X.X%)	XX	XX (X.X%)	XX								
()	XX (X.X%)	XX	XX (X.X%)	XX								

<sup>1 Numbers of adverse events

### 12.2.3 All TEAEs

Table TTT. TEAEs by SOC and PT

SOC	Placebo	4P004	4P004	4P004	4P004	4P004
PT	(pooled)					(pooled)
	(N=XX)	(N=XX)	(N=XX)	(N=XX)	(N=XX)	(N=XX)
Any TEAE	XX (XX.X%)					
SOC term	XX (XX.X%)					
PT term	XX (XX.X%)					
()	XX (XX.X%)					
SOC term	XX (XX.X%)					
PT term	XX (XX.X%)					
()	XX (XX.X%)					

Table TTT. TEAEs by SOC, PT and Toxicity Grade

SOC	Toxicity	Placebo	4P004	4P004	4P004	4P004	4P004
PT	Grade	(pooled)					(pooled)
		(N=XX)	(N=XX)	(N=XX)	(N=XX)	(N=XX)	(N=XX)
Any TEAE	1 Mild	XX (XX.X%)					
	2 Moderate	XX (XX.X%)					
	()	XX (XX.X%)					
SOC term	1 Mild	XX (XX.X%)					
	2 Moderate	XX (XX.X%)					
	()	XX (XX.X%)					
PT term	1 Mild	XX (XX.X%)					
	2 Moderate	XX (XX.X%)					
	()	XX (XX.X%)					
()							
SOC term	1 Mild	XX (XX.X%)					
	2 Moderate	XX (XX.X%)					
	()	XX (XX.X%)					
PT term	1 Mild	XX (XX.X%)					
	2 Moderate	XX (XX.X%)					
	()	XX (XX.X%)					
()		•	•	•	•	•	

With the same template, the TEAEs will be presented by Relationship to study drug, grouped as:

- Not related: No/Unlikely
- Related: Possible, Probable, Definite

#### Table TTT. TEAEs by SOC, PT and Relationship to Study Drug

#### 12.2.4 AESI

AESI defined in the protocol are:

- Pregnancy of the participant or of his partner
- Symptomatic overdose
- Anaphylaxis
- Severe IMP injection site reactions
- Hypoglycemia
- Severe gastro-intestinal disorder

All tables in the section "All TEAEs" will be reproduced for TEAEs of SI, except by relationship to study drug. All tables will also show the number of adverse events, as in the Overview of Adverse Events.

#### Table TTT. Treatment-Emergent AESIs by SOC and PT

### Table TTT. Treatment-Emergent AESIs by SOC, PT and Toxicity Grade

A listing of all treatment-emergent AESI will also be provided.

### **Listing LLL. Treatment-Emergent AESIs**

#### 12.2.5 Local tolerability

The AE details in case of severe IMP injection site reaction will be presented as follows:

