## 3.2 Endpoints

#### 3.2.1 Primary endpoints

- Number of Adverse events (AEs), serious AEs (SAEs) (Common Terminology Criteria Adverse Events [CTC-AE]) from ICF signature to D29, including target knee pain and tenderness, erythema, swelling, local pain at injection site.
- Vital signs from D-7 to D8, ECG from D-7 to D1: Mean change, number of Potentially Clinically Significant Abnormality (PCSA), Percentage of participants with PCSA
- Laboratory changes (Red Blood Cells (RBC), White Blood Cells (WBC), Hemoglobin (Hb), platelets, alanine transaminase (ALT), aspartate transaminase (AST), glycemia, amylasemia, creatinin clearance) from D-7 to D8: Mean changes number of PCSA, Percentage of participants with PCSA.

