#### 8.1.5 Local safety

The evaluation of IA injection site reaction following IMP administration will be performed by the Investigator or designees as outlined in section 1.2.2. Findings at the site of injection such as, but not limited to tenderness, erythema, and swelling, will be recorded in the eCRF in 3 different grades (mild/moderate/severe).

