### 10.1.4 Safety analysis

The safety evaluation will be based upon the review of the individual values (clinically significant abnormalities), descriptive statistics (summary tables, figures) and, if needed, on statistical analysis (appropriate estimations, confidence intervals). No statistical significance tests will be performed on safety data.

Potentially clinically significant abnormality (PCSA) values are defined as abnormal values considered medically important by the Sponsor, according to predefined criteria/thresholds based on literature reviews and defined by the Sponsor for clinical laboratory tests, vital signs, and ECG parameters.

All safety data will be presented in listings and will be summarized by placebo, each 4P-004 dose level, 4P-004 overall, and overall total.

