#### Local tolerability

The number (%) of participants with injection site reactions will be summarized overall and by maximum severity by treatment group. The incidence of AEs related to local tolerability findings will be summarized over time.

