**Table TTT. Injection Site Reactions** 

Kind of	Maximum	Placebo	4P004	4P004	4P004	4P004	4P004
Reaction	Toxicity	(pooled)					(pooled)
	Grade	(N=XX)	(N=XX)	(N=XX)	(N=XX)	(N=XX)	(N=XX)
Any Kind	Any Grade	XX (XX.X%)					
	1 Mild	XX (XX.X%)					
	2 Moderate	XX (XX.X%)					
	()						
Tenderness	Any Grade	XX (XX.X%)					
	1 Mild	XX (XX.X%)					
	2 Moderate	XX (XX.X%)					
	()						
Erythema	Any Grade	XX (XX.X%)					
	1 Mild	XX (XX.X%)					
	2 Moderate	XX (XX.X%)					
	()						
()	• •						

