#### 16 References

ICH Guidance Topic E9 "Statistical Principles for Clinical Trials"

# 17 Tables, Figures & Listings in CSR Section 14

The following tables will be included in the report either in the text or in a dedicated chapter reporting all tables but not included in the text.

Туре	Number	Title	Population
Table	1.1	Participant disposition	All
Table	1.2	Deviations by Category	Safety
Listing	1.2.1	Major Deviations	Safety
Table	1.3	Demographics and Baseline Characteristics	Safety
Table	1.4	Other Baseline Characteristics	Safety
Table	1.5.1	Pain killers started and ended before treatment	Safety
Table	1.5.2	Other medications started and ended before treatment	Safety
Table	1.6	Medical History by SOC	Safety
Table	2.1	Pain killers started before treatment and continuing at IMP injection	Safety
Table	2.2	Pain killers started during treatment	Safety
Table	2.3	Other medications started before treatment and continuing at IMP injection	Safety
Table	2.4	Other medications during treatment	Safety
Table	3.1	Overview of TEAEs	Safety
Table	3.1.1	TEAEs by SOC and PT	Safety
Table	3.1.2	TEAEs by SOC, PT and Toxicity Grade	Safety
Table	3.1.3	TEAEs by SOC, PT and Relationship to Study Drug	Safety
Table	3.2	Treatment-Emergent AESIs by SOC and PT	Safety
Table	3.2.1	Treatment-Emergent AESIs by SOC, PT and Toxicity Grade	Safety
Listing	3.2.2	Treatment-Emergent AESIs	Safety
Table	3.3	Injection Site Reactions	Safety
Listing	3.4	Serious Adverse Events	Safety
Listing	3.5	Deaths	Safety
Table	4.1	Target Knee Pain from Pre-Dose to 24h Post-Dose	Safety
Table	4.2	Target Knee Pain from Visit 2 to End of Study	Safety
Table	4.3	Target Knee Pain from Visit 2 to Day 8	Safety
Table	5.0	Weight over Time	Safety
Table	5.1	Systolic Blood Pressure over Time	Safety
Table	5.2	Diastolic Blood Pressure over Time	Safety
Table	5.3	Heart Rate over Time	Safety
Table	6.1	ECG: Heart Rate over Time	Safety
Table	6.2	ECG: PR over Time	Safety
Table	6.3	ECG: QRS over Time	Safety
Table	6.4	ECG: QT over Time	Safety
Table	7.1	Hematology over Time	Safety
Table	7.1.1	Hematology PCSA over Time	Safety
Table	7.2	Chemistry over Time	Safety
Table	7.2.1	Chemistry PCSA over Time	Safety
Table	7.3	Glycemia over Time	Safety
Table	8.1	Plasma Concentrations over Time	PK
Figure	8.1.0.3	Plasma Concentrations over Time by Subject -	PK
Figure	8.1.1	Plasma Concentrations over Time by Subject -	PK
Figure	8.1.2	Plasma Concentrations over Time by Subject -	PK
Figure	8.1.3	Plasma Concentrations over Time by Subject -	PK

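### The lead-in to SAP 12.2.5 limits the injection-site reaction table to severe reactions, against its own shell and protocol 10.1.4; the data source, a listing and the over-time summary are also missing

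*SAP*

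**What the plan says.** **Protocol.** Section 3.2.1 defines the first primary endpoint as a count of adverse events, "including target knee pain and tenderness, erythema, swelling, local pain at injection site". Section 8.1.5 has the investigator or a designee evaluate the injection site; findings "will be recorded in the eCRF in 3 different grades (mild/moderate/severe"). The D1-D2 flowchart (1.2.2) gives local reaction its own row, separate from the adverse event row, at 1, 2, 3, 4, 5 and 24 hours after injection. On analysis, section 10.1.4 makes three commitments:

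- under Local tolerability, "The number (%) of participants with injection site reactions will be summarized overall and by maximum severity by treatment group";
- under the same heading, "The incidence of AEs related to local tolerability findings will be summarized over time";
- for safety data in general, "All safety data will be presented in listings and will be summarized by placebo", each dose level and the pooled groups.

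**SAP.** Section 12.2.5 opens with "The AE details in case of severe IMP injection site reaction will be presented as follows". The shell below it, "Table TTT. Injection Site Reactions", is laid out by kind of reaction (any kind, tenderness, erythema and so on) and by maximum toxicity grade, with rows for any grade, mild, moderate and a continuation. Section 17 indexes it as Table 3.3, "Injection Site Reactions", on the Safety population, with no severity limit in the title. Section 18 has 20 listings. These include adverse events (16.2.9), knee pain (16.2.10), vital signs (16.2.12) and ECG (16.2.13), but none for local reaction assessments.

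**The concern.** The lead-in is the only sentence in the SAP that says what goes into Table 3.3, and it names adverse event details for severe reactions only. That is narrower than the protocol's commitment. The word severe matches the AESI category in SAP 12.2.4, so the AESI restriction may have been carried into local tolerability by accident. The documents do not settle this.

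Protocol 2.3 says that no human safety data exist for intra-articular injection, so local tolerability is among the main new questions of the trial. With six active participants per cohort and no significance tests, description is all the analysis offers. A few mild or moderate reactions clustering at one dose is the sort of pattern the table should show. If two programmers can build different tables from the same section, that display is not fixed in advance.

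**Working it through.** The plan gives no figure to reproduce on this point, and no power or error-rate calculation applies. The check compares texts and makes one count.

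**1. Lead-in against shell.** Suppose Table 3.3 held only participants with a severe reaction. Each of them would have a maximum grade, over all kinds, of severe or worse. In the any-kind block the mild and moderate rows would then be zero by construction, and the any-grade row would equal the number with a severe or worse reaction. (Within a single kind a mild row could still be filled, for example mild tenderness in someone with severe erythema.) A shell that prints mild and moderate rows for any kind was not designed for that population, so sentence and shell cannot both be literal.

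**2. Lead-in against protocol.** Protocol 10.1.4 asks for participants with reactions overall and by maximum severity. The shell delivers this; the lead-in, read literally, does not. As an illustration on assumed numbers, if 4 of 6 participants at a dose had moderate swelling as their worst reaction, Table 3.3 would show 0/6 under the literal reading and 4/6 under the shell's reading.

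**3. Data source.** The terms AE details and Toxicity Grade in SAP 12.2.5 point to adverse event records, which protocol 8.2 and 11.3.4 grade on the five-grade DAIDS table. The kinds of reaction in the shell match the findings graded on three levels under protocol 8.1.5. The SAP does not choose between them or say how the scales are combined.

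**4. Volume without a listing.**

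- Scheduled assessments per participant (protocol 1.2.2): 1, 2, 3, 4, 5 and 24 h = 6.
- Planned participants (protocol 1.1): 32, giving 6 × 32 = 192.
- With the ninth cohort 3 participant (SAP 9.3): 6 × 33 = 198.

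None of these has a dedicated listing among the 20 in SAP section 18, although protocol 10.1.4 says all safety data will be listed.

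**5. Over-time summary.** Protocol 10.1.4 plans the incidence of local-tolerability adverse events over time. Neither SAP 12.2.5 nor the table index in section 17 contains such a summary.

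**6. What still reaches the outputs.** Reactions of any grade recorded as treatment-emergent adverse events enter the overview (Table 3.1), the SOC/PT table (3.1.1), the table by toxicity grade (3.1.2) and Listing 16.2.9. Severe ones also enter the AESI tables.

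**The case against.** The strongest reply is that the shell and the unrestricted title of Table 3.3 already show the intent: all grades, by kind and maximum severity, much as the protocol asks. On that view the lead-in is a slip. The primary endpoint is itself a count of adverse events, and the protocol's over-time sentence also concerns adverse events, so building Table 3.3 from adverse event records would not in itself depart from the endpoint.

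Much of this stands, and it rules out several stronger readings that a reader might infer:

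- *That graded local findings reach no table or listing.* Table 3.3 may well be meant to hold them, and any entered as adverse events appear in the outputs named in step 6.
- *That the report would show few or no reactions even if mild or moderate ones rose with dose.* This ignores the TEAE tables by grade and Listing 16.2.9.
- *That counting depends on whether sites enter a finding twice.* The documents do not show the eCRF layout. Protocol 11.3.1 defines an adverse event broadly enough to include an unfavourable sign, and 11.3.4 provides a solicited/unsolicited descriptor, which is consistent with local findings being entered as adverse events. However, 11.3.1 also ties abnormal safety assessments to the investigator's judgment of clinical significance, and neither document says every graded finding must become an adverse event. The question is open either way.
- *That the protocol promises an hourly table.* Section 10.1.4 names no time points; the grid comes from the assessment schedule.

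The reply does not answer the contradiction in the text, the unstated source, the missing listing or the missing over-time summary.

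**Conclusion.** The point holds in a limited form. The lead-in to SAP 12.2.5 contradicts its own shell and protocol 10.1.4. Taken literally, it removes participants with at most mild or moderate reactions from the only table devoted to injection-site reactions. Three gaps accompany it: no stated data source or grading scale for Table 3.3, no listing for the 192 (or 198) scheduled local assessments, and no over-time summary.

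That count assumes every participant completes all six assessments. It measures scheduled data without a dedicated listing; it does not measure lost information, because Table 3.3 could still summarise those data by maximum grade. How many reactions would go unreported cannot be derived from the documents. It depends on which reading the programmer adopts and on how local findings are entered in the eCRF. The correction should be made because the wording, as it stands, permits the wrong table for a component of the primary endpoint.

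**What to change.** 1. In SAP 12.2.5, delete the restriction to severe reactions. State that Table 3.3 shows the number and percentage of participants with an injection-site reaction of any grade, by kind and maximum severity.
2. Name the source: the scheduled local assessments together with injection-site adverse events, each participant counted once at the highest grade. State the grading scale and how the three-grade assessments line up with the DAIDS grades of the adverse event records.
3. Add a section 16.2 listing of local reaction assessments by participant and time point.
4. Add the over-time summary planned in protocol 10.1.4. The flowchart times (1, 2, 3, 4, 5 and 24 h) are a natural choice, but the protocol does not name them for this purpose, so the SAP should specify them.
5. Keep severe reactions in the AESI tables.

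The cost is one reworded paragraph, one revised table, one added summary and one added listing, all from data already collected. Study conduct is unaffected.
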